11.7 Software

Pharmacokinetic parameters will be derived using noncompartmental methods with the validated computer program Phoenix® WinNonlin® 6.4 or higher (PPD [REDACTED]). Pharmacokinetic figures will be developed by Phoenix® WinNonlin® 6.4 or higher, or SAS® Windows Version 9.4 or higher (PPD [REDACTED]).

All other statistical analyses will be conducted using SAS® Version 9.4 or higher.

11.8 Definition of baseline

Unless otherwise specified, baseline for end of study is defined as the last non-missing measurement taken prior to or on the day of the first IMP administration (including unscheduled assessments as applicable). However, if time is missing, an unscheduled assessment on study day 1 will be considered to have been obtained after study treatment administration.

For vital signs, the assessment performed within 1 hour (± 30 minutes) prior to IMP administration in each treatment period will be considered as baseline for the treatment period. If there is no time point, the last non-missing assessment prior to dosing in each period will be taken as baseline.

In the case where the last non-missing measurement and the dosing date/time coincide, that measurement will be considered baseline, but medications commencing on the first IMP administration date will be considered post-baseline.

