1.3 Schedule of Activities

Table 1 Schedule of Assessments

Assessments	Screening (Baseline)		Period 1			7	Period 2			Conditional Follow-up Visit or Premature Withdrawal ^k
	-14 to -2	-1	1	2	3		8	9	10 ^j	
Day ^a	-14 to -2	-1	1	2	3	7	8	9	10 ^j	15 (or specific day)
Informed consent form signed	X									
Inclusion/exclusion criteria	X	X								
Demographic information ^b	X									
History of alcohol and nicotine consumption	X									
Medical history	X	X								
Prior medications ^c	X	X								
Laboratory tests (including blood and urine tests)	X	X						X		X
Pregnancy test ^d (women of childbearing potential)	X	X								
HAV antibody, HBsAg, HCV antibody, HIV antibody, and TP antibody tests	X									
Urine drug abuse test and breath test of alcohol	X	X								
Urine nicotine	X									
Randomization		X								
Drug administration			X				X			
Meal recording			X				X			
Blood sampling for pharmacokinetics ^e			X	X	X		X	X	X	X ^e
Physical examination ^f	X	X		X	X			X		X
Vital signs ^g	X	X	X ^g				X ^g		X ^g	X
Electrocardiogram	X	X	X ^h				X ^h		X ^h	X
Chest X-ray	X									
AE recording ⁱ		X	X	X	X	X	X	X		X
Concomitant therapy recording			X	X	X	X	X	X	X	X

AE= adverse event; BMI= body mass index; HAV= hepatitis A virus; HBsAg= hepatitis B surface antigen; HCV= hepatitis C virus; HIV= human immunodeficiency virus; IMP = investigational medicinal product; PK = pharmacokinetic; TP = Treponema pallidum.

a. Participant will participate in the clinical study on an inpatient basis during Day -1 to Day 10.

b. Demographic data include: date of birth, sex, race, height, and weight. The BMI (kg/m^2) will be calculated automatically.

c. Prior medications within 30 days before the date of first signature of informed consent will be collected at the screening visit. Medications administered before the first IMP dose will also be recognized as prior medication and used for eligibility check.

d. Serum pregnancy test will be done at screening and at Day -1.

- e. See [Table 6](#) for a detailed schedule of sampling during the inpatient at the research center. There will be an extra PK sampling for participants with premature withdrawal; for participants having conditional follow-up visit for safety, no PK sampling is required.
- f. Physical examination includes assessments of the general appearance, skin and mucosa, superficial lymph nodes, head and neck, chest, abdomen, musculoskeletal, and neurological systems.

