- g. Vital signs including blood pressure (systolic and diastolic pressures), pulse rate, body temperature, and respiration (frequency per minute) will be measured and recorded. Blood pressure and pulse rate will be recorded in a sitting position after the participant has rested comfortably for at least 5 minutes (The blood pressure normal range is considered ≥ 90 mmHg and ≤ 139 mmHg for systolic blood pressure; ≥ 60 mmHg and ≤ 90 mmHg for diastolic blood pressure)). At Day 1 and Day 8, vital signs will be measured 1 hour (± 30 minutes) prior to dosing and at 4 hours (± 30 minutes) postdose. Vital signs will also be assessed at Day 10.
- h. Electrocardiogram (12-lead electrocardiogram, including QTc evaluation) will be performed 4 hours (± 30 minutes) postdose at Day 1 and Day 8. Electrocardiogram will also be performed at Day 10 before discharge from the research unit.
- i. Adverse events will be collected starting from Day -1. At Day -1, the AEs since the date of signing of informed consent will be recorded; the subsequent visits will record any AEs since the last visit.
- j. Participants will be discharged on Day 10, after final sample collection and safety examinations are completed (final examination).
- k. If a participant has ongoing AE at End-of-Study discharge on Day 10, the participant must come back for the follow-up visit.

1.4

Estimated Blood Sample Volumes per Participant

The blood sample volumes of each participant are estimated in [Table 2](#).

Table 2 **Estimated Blood Sample Volumes per Participant**

Time Points	Evaluation Indexes	Total Blood Volume (mL)
Screening (including Randomization)	Serum virology	4
	Hematology	2*2
	Biochemistry	4*2
	Serum Pregnancy Test (if applicable)	4*2
	Subtotal	24 (16 for male)
Period 1	Pharmacokinetics	3*17
	Subtotal	51
Period 2	Hematology	2
	Biochemistry	4
	Pharmacokinetics	3*17
	Subtotal	57
Conditional follow-up Or Premature withdrawal	Hematology	2
	Biochemistry	4
	Subtotal	6
	Pharmacokinetics (only for premature withdrawal)	3
Approximate Total Amount of Blood for Each Participant		132 (124 for male) With conditional follow-up: 138 (130 for male)

2 Introduction

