7.2 Randomization

Each eligible participant will be allocated to a treatment sequence according to a computer-generated randomization schedule. Subjects will be identified only by their assigned participant number. The participants will receive consecutive participant numbers in the order of their enrollment into the study.

A total of 54 eligible healthy male and female Chinese participants (38 in fasting group and 16 in fed group, Table) who meet the eligibility criteria will be randomized (with each gender representing no less than 1/4 of the total number within each group, i.e., no less than 10 participants

of each gender in the fasting group and no less than 4 in the fed group) on Day 1, in a 1:1 ratio to 1 of 2 treatment sequences: Sequence A-B or Sequence B-A as presented in Table .

Sequence A to B:

- Day 1 (Period 1), Treatment A: the administration of a single dose of test GXR
- Day 8 (Period 2), Treatment B: the administration of a single dose of reference GXR

Sequence B to A:

- Day 1 (Period 1), Treatment B: the administration of a single dose of reference GXR
- Day 8 (Period 2), Treatment A: the administration of a single dose of test GXR

The 2 doses will be separated by a Washout period of approximately 7 days ([Table 7](#)).

Table 5 Randomization Allocation

	Day 1	Day 8
Fasting group (n= 38)	Treatment A (n= 19)	Treatment B (n= 19)
	Treatment B (n= 19)	Treatment A (n= 19)
Fed group (n= 16)	Treatment A (n= 8)	Treatment B (n= 8)
	Treatment B (n= 8)	Treatment A (n= 8)

Table 6 Assignment to Administration Sequences

	Day 1	Day 8
Sequence A to B	GXR 500 mg (Merck Nantong manufactured) (Test Product)	GXR 500 mg (Merck Darmstadt manufactured) (Reference Product)
Sequence B to A	GXR 500 mg (Merck Darmstadt manufactured) (Reference Product)	GXR 500 mg (Merck Nantong manufactured) (Test Product)

GXR=Glucophage® Extended Release.

Table 7 Instruction of Study Periods

Screening Period	Randomization	Treatment Period 1	Washout Period	Treatment Period 2	End-of-Study Discharge	Conditional Follow-up

Day -14 to Day -1	Day -1	Day 1 to Day 3 Inpatient	7 days Inpatient	Day 8 to Day 10 Inpatient	Day 10	Day 15
----------------------	--------	-----------------------------	---------------------	------------------------------	--------	--------

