11.15 Trial day

Trial day will be calculated from the reference start date, and will be used to show start/end day of assessments and events. Reference start date is defined as the day of the first IMP administration in period 1. Trial Day 1 is the day of first IMP administration in period 1. The day before is defined as Trial Day -1 (no Trial Day 0 is defined). Trial day will be calculated accordingly:

- If the date of the event is on or after the reference start date then:

Trial day = (date of event – reference start date) + 1.

- If the date of the event is prior to the reference start date then:
Trial day = (date of event – reference start date).

12 Trial Subjects

This section includes specifications for reporting subject disposition and treatment/trial discontinuations. Additionally, procedures for reporting protocol deviations are provided.

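### SAP 11.8 sets the end-of-study baseline cut-off by calendar day, so as written it selects the Day 1 ECG taken 4 hours after dosing as baseline

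*SAP*

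**What the plan says.** The first sentence of SAP 11.8 gives the general rule, which applies unless something else is specified: "baseline for end of study is defined as the last non-missing measurement taken prior to or on the day of the first IMP administration". SAP 11.15 identifies that day: "Trial Day 1 is the day of first IMP administration in period 1".

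The rest of 11.8 adds three provisions:

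- Untimed values: "if time is missing, an unscheduled assessment on study day 1 will be considered to have been obtained after study treatment administration".
- Ties: "In the case where the last non-missing measurement and the dosing date/time coincide, that measurement will be considered baseline".
- Vital signs only: the assessment about 1 hour before dosing in each period "will be considered as baseline for the treatment period".

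On timing, footnote h to Table 1 in Protocol 1.3 says the ECG "will be performed 4 hours (± 30 minutes) postdose at Day 1 and Day 8". The other scheduled ECGs are at screening, Day -1 and Day 10, and at the follow-up or withdrawal visit where that applies. Table 1 attaches the word baseline to its screening heading.

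SAP 17.5.1 summarises the ECG parameters at baseline and at the end-of-study visit, by sequence and overall within each food group. It does not define an ECG baseline of its own.

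**The concern.** A baseline safety value should be an untreated value. The general rule admits anything measured on the day of first dosing and then takes the last such value. For ECG that is a value obtained under treatment, and the treatment differs by sequence. SAP 7.2 describes Sequence A-B as starting with "Day 1 (Period 1), Treatment A: the administration of a single dose of test GXR"; Sequence B-A starts with the reference product. One sequence's baseline column would then describe ECGs after test, the other's ECGs after reference, and the end-of-study values would have no untreated summary beside them.

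The untimed-value and tie rules point the other way. A programmer following the opening sentence and one following the implied cut-off would flag different records, each with support in the text. The SAP exists to prevent that kind of divergence.

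**Working it through.** The documents give no figure to reproduce. The check applies both readings of 11.8 to the scheduled assessments in Protocol Table 1 (footnotes g and h).

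- **Reading A (opening sentence as written):** last non-missing value with trial day ≤ 1.
- **Reading B (cut-off implied by the untimed-value and tie rules):** last non-missing value at or before the first dose.

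| Assessment | Scheduled up to and including Day 1 | Reading A | Reading B |
|---|---|---|---|
| ECG | Screening; Day -1; Day 1 at +4 h | Day 1, +4 h | Day -1 |
| Vital signs | Screening; Day -1; Day 1 at -1 h and +4 h | Day 1, +4 h | Day 1, -1 h |
| Laboratory | Screening; Day -1 | Day -1 | Day -1 |

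**ECG.** With the ±30-minute window, Reading A selects a value 3.5 to 4.5 hours after dosing. The two readings disagree for every participant who has both the Day -1 and the Day 1 ECG.

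**Why the rest of 11.8 implies Reading B.** Treating an untimed unscheduled Day 1 value as post-dose has a purpose only if post-dose values are ineligible; under Reading A the assumption would not exclude the value. A tie rule at the moment of dosing is likewise unnecessary if the whole day qualifies.

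**Vital signs.** The vital-sign paragraph supplies a pre-dose baseline, but for the treatment period. SAP 17.4 also tabulates vital signs at baseline and end of study. Whether the paragraph counts as an exception for that second table is not stated, so this is an ambiguity rather than a wrong rule.

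**Participants affected (SAP Table 5):**

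- Sequence A-B, ECG 4 h after test: 19 fasting + 8 fed = 27
- Sequence B-A, ECG 4 h after reference: 19 fasting + 8 fed = 27
- Total: 27 + 27 = 54, if all planned participants are dosed and have the Day 1 ECG

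**Summaries affected (SAP 17.5.1):** there are 7 continuous parameters (RR, PR, QRS, QT, QTcB, QTcF, heart rate); rhythm is categorical and left out.

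- Baseline summaries: 7 parameters × 2 food groups × 3 columns (A-B, B-A, overall) = 42
- All continuous summaries: 42 × 2 visits = 84
- Share affected: 42 of 84

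**Primary analysis:** 2 endpoints × 2 food groups = 4 bioequivalence comparisons. None uses this baseline.

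**The case against.** The strongest reply is that the opening sentence should not be read alone. The next sentence qualifies it, the tie rule compares with the dosing date and time, and together they show what was meant. SAP 11.2 sorts post-baseline time points under the treatment most recently received, and SAP 13.3 groups ECG with baseline characteristics; both fit a pre-dose ECG baseline. SAP 11.15 defines trial day for display purposes and does not itself govern baseline eligibility. The table shells are not in the supplied text and may name the baseline visit. Every ECG is also listed by visit, treatment and time point, so the Day -1 and Day 1 values remain distinguishable.

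Much of this stands as evidence of intent: the authors very probably wanted a pre-dose baseline. It does not change the operative sentence, which still gives the post-dose ECG when followed. SAP 11.2 is a listing rule, 13.3 sets no cut-off, and 11.15 is needed only to identify the day. The point about the shells is a real limit: the finding concerns the supplied text.

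Two points on size are also fair. The 42 of 84 is a count of table entries, not a measure of bias. And 54 is the planned number; replacements under SAP 7.2 could raise the number dosed.

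**Conclusion.** The concern holds, and it is minor. As written, the general rule in SAP 11.8 selects the 4-hour post-dose Day 1 ECG as the end-of-study baseline, while the untimed-value and tie rules in the same section imply a cut-off at dosing, which gives the Day -1 ECG.

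The consequence is confined to descriptive safety tables: the ECG baseline column and, depending on how the exception is read, the vital-sign baseline column in 17.4. No size of bias is claimed. The documents give no ECG effect of the product, 17.5.1 plans no ECG change from baseline, and its ECG frequency table is for end of study only.

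The conclusion assumes that ECGs are taken as scheduled, with no unscheduled pre-dose ECG entering on Day 1, and that no shell outside the supplied text sets a different ECG baseline.

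**What to change.** In the opening sentence of SAP 11.8, replace the day-based limit so that the rule reads: *baseline for end of study is the last non-missing measurement taken at or before the date and time of the first IMP administration*. Keep the existing opening qualifier and the parenthesis on unscheduled assessments, since the vital-sign exception and the untimed-value rule build on them. The revised sentence agrees with the tie rule and yields the Day -1 ECG and the Day 1 pre-dose vital signs.

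Add one sentence to the vital-sign paragraph saying that the Period 1 pre-dose value is also the baseline for the end-of-study table in 17.4. Leave the period-specific pre-dose baseline as it is.

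The cost is one or two sentences in the SAP and the matching ADaM baseline flag. No new data or assessments are needed.

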11.9 Definition of End of Study

Unless otherwise specified, end of study is defined as the last measurement taken prior to or on the day of discharge (Day10 or any special day for Premature Withdrawal Visit).

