9.4 Statistical Analyses

9.4.1 General Considerations

Details of the statistical analysis will be presented in a statistical analysis plan prior to database lock.

The statistical analysis will not be started until all data have been corrected and checked for plausibility, and until all necessary coding and assessments have been completed.

All data recorded during the study will be presented in individual data listings performed on the Screening or Safety Population. All data will be evaluated as observed values; no imputation method for missing values will be used, unless otherwise stated. Methods for concentration data below the lower limit of quantification will be described in the statistical analysis plan.

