17.3 Clinical Laboratory Evaluation

Results from the central laboratory will be included in the reporting of this study for hematology, biochemistry, and urinalysis. Laboratory evaluations to be included in the outputs are as below:

Hematology: Erythrocytes, Hemoglobin, Hematocrit, Mean corpuscular volume, Mean corpuscular hemoglobin, Mean corpuscular hemoglobin concentration, Red blood cell distribution width, Platelets, Mean platelet volume, Thrombocytocrit, Platelet distribution width, White blood cells, Neutrophils (both percentage and absolute counts), Monocytes (both percentage and absolute counts), Lymphocytes (both percentage and absolute counts).

Biochemistry: Alanine Aminotransferase (ALT), Aspartate Aminotransferase (AST), Total Bilirubin, Total Bilirubin, Direct Bilirubin, Indirect Bilirubin, Protein total, Albumin, Globulin, Albumin/globulin ratio, Alkaline Phosphatase, Glutamyl Transpeptidase, Urea Nitrogen, Creatinine, Cholesterol, Triglycerides, Glucose, Creatine Kinase, Creatine Phosphokinase MB Isoenzyme, Lactate Dehydrogenase, Calcium, Phosphorus, α -Amylase, Sodium, Potassium, Chloride.

Urinalysis: Appearance, Blood, Nitrite, Ketone, Protein, Glucose, Leukocytes, pH, Microscopic examination (Microscopic examination will be performed if dipstick test is positive for leukocytes, blood, nitrites, or proteins).

All hematology, biochemistry and urinalysis quantitative parameters will be summarized using descriptive statistics overall and by treatment sequence for each group at baseline and at end of study visit with raw data and change from baseline.

For all hematology and biochemistry parameters, frequency tables based on the classification of values as Low, Normal, High and Missing with respect to the reference ranges will be summarized by treatment sequence at baseline and end of study for each group. Frequency tables of urinalysis will be summarized by treatment sequence at baseline and end of study for each group, based on different types of classification rules. For urinalysis parameter, pH, the classification of values as Low, Normal, High and Missing will be applied. For urinalysis parameters, Blood, Nitrite, Ketone, Protein and Glucose, the classification of values as Normal/-, +-, +, ++, +++, +++++ will be applied. For urinalysis parameters, Appearance and Microscopic Examination, the classification of values

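### SAP 11.9 picks the end-of-study safety value with no postdose or visit condition, so read literally a missed final assessment is filled by an earlier reading

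*SAP*

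**What the plan says.** SAP 11.9 states that, unless otherwise specified, "end of study is defined as the last measurement taken prior to or on the day of discharge". The discharge day is given in brackets as "Day10 or any special day for Premature Withdrawal Visit". The section sets no earliest time, names no visit for each type of assessment and does not require the value to follow a dose.

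SAP 11.8 supplies the comparator: "baseline for end of study is defined as the last non-missing measurement taken prior to or on the day of the first IMP administration".

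These two definitions feed the safety tables. SAP 17.3 summarizes laboratory parameters "at baseline and at end of study visit with raw data and change from baseline", and adds frequency tables and baseline-to-end-of-study shift tables. SAP 17.4 and 17.5.1 use end of study for vital signs and ECG. The frequency tables in these sections generally carry a Missing class.

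Protocol 9.4.1 plans to evaluate data as observed and says that "no imputation method for missing values will be used, unless otherwise stated". SAP 9 declares no changes to the planned analyses.

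The schedule is in Protocol 1.3, Table 1. The row that begins "Laboratory tests (including blood and urine tests" is marked at screening, Day -1, Day 9 and the Day 15/withdrawal column. For Days 1 and 8, note g says that "vital signs will be measured 1 hour (± 30 minutes) prior to dosing and at 4 hours" postdose, with a further assessment on Day 10. Note h puts the ECG at 4 hours postdose on Days 1 and 8, and adds: "Electrocardiogram will also be performed at Day 10 before discharge from the research unit".

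**The concern.** SAP 11.9 works as a selection rule: it tells the programmer which measurement to use. Because it has no lower bound, it returns a value whenever any earlier measurement exists, including one taken before the first dose. A participant with no postdose laboratory result would then appear in the change and shift tables as if measured and unchanged. In the vital-sign and ECG tables, a reading taken 4 hours after dosing would stand in the same column as Day 10 discharge readings.

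The SAP does not call this imputation, so the flag that SAP 11.14 requires for imputed values would not be triggered. At stake is whether the end-of-study safety tables show what was observed at end of study. The primary endpoints are not involved.

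**Working it through.** The plan gives no figure on this point to reproduce. The check applies SAP 11.9 as written to the Table 1 schedule with the final assessment removed, and then sizes one such case.

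**Step 1. Which value the rule returns.**

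| Assessment | Scheduled from Day -1 to Day 10 | Final | Returned if the final one, and any withdrawal assessment, is absent |
|---|---|---|---|
| Laboratory | Days -1, 9 | Day 9 | Day -1, predose |
| Vital signs | Days -1, 1, 8, 10 | Day 10 | Day 8, 4 h postdose; Day 1, 4 h postdose, for someone who left before Day 8 |
| ECG | Days -1, 1, 8, 10 | Day 10 | as for vital signs |

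**Step 2. Laboratory change.** The Day -1 panel is normally the last one up to the first dosing day, so SAP 11.8 makes it the baseline. Change = end-of-study value - baseline = Day -1 value - Day -1 value = 0, and the shift-table entry falls on the diagonal.

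**Step 3. Whether another section blocks this.** SAP 11.10 limits visit statistics to scheduled visits, but Day -1 and Day 8 are scheduled. SAP 11.14 contains no rule for laboratory, vital-sign or ECG values. The Missing class in SAP 17.3 to 17.5.1 implies that an absent value stays absent. Under SAP 11.9 as written, however, the laboratory class would be almost empty, because everyone randomized should have a Day -1 panel. The two cannot both operate as written, and no section says which prevails.

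**Step 4. Size of one case.** SAP 7.2 plans n = 8 per sequence in the fed group and n = 19 in the fasting group. Suppose m participants carry a forced zero and the other n - m have mean change d. Then:

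reported mean = [(n - m) x d + m x 0] / n = d x (1 - m/n)

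- Fed, m = 1: 1/8 = 12.5%, factor 0.875.
- Fasting, m = 1: 1/19 = 5.3%, factor 0.947.
- Fed, m = 2: 2/8 = 25.0%, factor 0.750.
- Fasting, m = 2: 2/19 = 10.5%, factor 0.895.

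The m = 2 lines only illustrate the formula; the documents give no expected number of missed panels.

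**Step 5. Whether a postdose condition alone would be enough.** For laboratory tests it would, provided it refers to the participant's last dose. For vital signs and ECG it would not, because the Day 8 reading at 4 hours is already postdose. Those need a named assessment.

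**The case against.** The best counter-argument is that carrying values forward was never intended, and much of the text supports it:

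- SAP 17.3 to 17.5.1 refer to an end-of-study visit and provide a Missing class.
- SAP 11.6 shows missing observations as a separate category.
- SAP 11.13 says that, unless otherwise specified, data from discontinued participants are not replaced.
- SAP 11.8 specifies a non-missing measurement; SAP 11.9 does not use that qualifier.
- Allowing measurements before the discharge day has an innocent purpose: the last laboratory panel is on Day 9 and discharge is on Day 10.
- Protocol 9.4.1 permits exceptions to its no-imputation rule, so the conflict with it is not absolute.

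This stands as evidence of intent, and the point is best seen as a drafting gap. It does not remove the gap, because none of these passages overrides the explicit rule in SAP 11.9.

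The trigger is also narrow. Participants are inpatients from Day -1 to Day 10, Protocol 7.4 requires the withdrawal assessments, and SAP 11.3 admits repeats made for technical reasons such as clotted samples. That stands too, and it limits the size of the problem.

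A reader might infer more than the documents support:

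- **That the error always reassures.** It pulls toward no change, which would also hide an improvement. Inclusion criterion 7 admits out-of-range values judged not clinically relevant, so a carried value may itself be abnormal.
- **That these tables are the only laboratory safety output.** SAP 17.3 also plans a listing of marked abnormalities and full listings by visit and time point, where an absent Day 9 result would show.
- **That the replacement thresholds of 28 and 12 forecast the loss.** They concern participant numbers, not missed laboratory samples.

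**Conclusion.** The point holds as a conflict between a stated selection rule and the tables it feeds. Read literally, SAP 11.9 assigns a predose laboratory value to a participant with no Day 9 and no withdrawal panel, giving zero change and no shift. It also substitutes an earlier reading for a missed Day 10 vital-sign or ECG assessment.

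Per case, the sequence's mean laboratory change moves toward zero by 12.5% (fed) or 5.3% (fasting). This assumes full planned sequence sizes, all other participants measured, and Day -1 as the baseline.

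The practical effect should be small. Cases should be rare, only descriptive safety summaries are touched, the listings would still reveal the gap, and the bioequivalence conclusion does not depend on it. It is still worth correcting, because a programmer following the text would produce a wrong value.

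**What to change.** Restate SAP 11.9 along these lines: the end-of-study value is the measurement from the Period 2 end-of-study assessment (Day 9 for laboratory tests; Day 10 for vital signs and ECG) or from the Premature Withdrawal visit, taken after the participant's last IMP administration. Repeats done for technical reasons under SAP 11.3 are included. The 4-hour postdose readings are not eligible. If no such measurement exists, the value is Missing and is counted in that category.

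Two details matter. Simply deleting the allowance for measurements before the discharge day would lose the Day 9 panel. Restricting the rule to scheduled measurements without the SAP 11.3 exception could bar valid repeats.

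The cost is a short rewrite of one SAP section and a filter in the derivation. The end-of-study N may fall slightly. SAP 11.6 already provides for showing missing observations separately.
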